4 MATERIALS AND METHODS

4.1 STUDY DESIGN

4.1.1 OVERALL DESIGN

This study is a prospective, double-masked (investigator and participant), bilateral, randomized, cross-over dispensing study comparing subject acceptance of BT test lens against UT control lens.

Both test and control lenses will be used in their approved daily lens wear modality for approximately one (1) month. It is anticipated that this study will involve up to 5 scheduled visits:

Visit 1: Includes screening, baseline assessments, fitting of both lens types.

Visit 2: Dispense lens pair #1 (either test or control lens).

Visit 3: 1-month follow-up visit of lens pair #1

Visit 4: Dispense of lens pair #2 (either test or control lens)

Visit 5: 1-month follow-up visit of lens pair #2 and study exit.

The study design in shown in Figure 1.

[figure not shown]

Figure 1: Study Design

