4.1.2 RANDOMIZATION

A randomization schedule will be generated using SAS or a web-based program: (www.randomization.com). An example of the format generated is given in Appendix 23. The final study randomization schedule will be generated by the CORE Data Management Team, and provided to the research assistants for use during the study. Study investigators will remain masked to the randomization schedule until the study is completed and the database is locked.

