4.6 STUDY POPULATION

4.6.1 NUMBER OF PARTICIPANTS

Up to 30 participants will be dispensed / randomized with study products, with a target of 26 completing the study. Participants will be recruited using CORE records and advertising approved by the UW Office of Research Ethics (Appendices 2, 3a, and 3b). Each participant will be given a unique study specific ID number. Additionally, all participants must meet all the study inclusion and none of the exclusion criteria listed below.

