11 STATISTICAL ANALYSIS AND DATA MANAGEMENT

11.1 SAMPLE SIZE CALCULATION

Sample size was calculated using the mean comfort rating data from the previous pilot PIANO study (EX-MKTG-83). The data from the PIANO-2 will be pooled with data from the pilot PIANO study, therefore anyone who participated in the pilot study will be excluded from participating in the PIANO-2 study.

A total sample size of 44 is recommended to provide a minimum power of 90 with an alpha of 0.05 in a two-tailed t-test to detect a difference of 1 comfort unit (scale of 0-10). Based on the results from the pilot study (i.e. PIANO Study) the sample size needed for PIANO-2 will be aimed at 26 to complete (i.e. total of 44 minus the 18 completed participants from the pilot study). Therefore, it is recommended that at least 30 subjects are dispensed in the PIANO-2 study, with a target of 26 to complete.

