11.2 STATISTICAL ANALYSIS

All data will be analyzed by CORE at the University of Waterloo. Data analysis will be conducted using Statistica, SPSS or SAS. Descriptive statistics will be provided on information regarding baseline variables (age, gender, refractive error distribution, etc.). Analysis of variables will be conducted separately on each eye, and data will not be pooled. For assessments conducted for each eye separately, the right eye will be used for analysis if there is no difference between eyes. If a general difference is found (e.g. for paired t-test / Wilcoxon matched pairs) between OD and OS, a comment will be provided.

A Binomial test will be used to analyze the results for the count data of subjective preferences. The number of "no preference" will be evenly distributed to the two options on the basis they would be equally likely to choose either.

Table 4 lists the primary study measures and anticipated statistical procedures.

Table 4: Study measures and anticipated statistical procedures

Variable	Analysis	Statistical test	
Analogue scales/Numeric scales/Preference scales/VA Lens parameters Biomicroscopy (continuous variables)	Effect of lens type	RMANOVA/MANOVA/ Friedman Wilcoxon matched pairs test Tukey HSD post hocs Paired t-test Chi-square test	
Biomicroscopy (ordinal variables)	Effect of lens type	Friedman Wilcoxon matched pairs test	
Analogue scales/Numeric scales/Lens parameters, Biomicroscopy (continuous)	Relationship between slit lamp findings and analogue scales	Pearson correlation - r	
Biomicroscopy (ordinal variables)	Relationship between slit lamp findings and analogue scales	Spearman correlation - rho	

The critical alpha level for statistical significance will be set at $p \le 0.05$, with no adjustments for multiple comparisons.

All participants who were evaluated will be used in the analysis. In the event of missing data, individual data points will be excluded in the analysis and not extrapolated from the collected data.

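### Section 11.2 specifies no period term for the crossover ratings and ignores lens order in the preference test; the planned tests stay valid on average, so this is a cheap improvement of low severity

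*Combined protocol and SAP*

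**What the plan says.** Section 4.1.1 describes a "randomized, cross-over dispensing study comparing subject acceptance of BT test lens against UT control lens". Each participant wears both lenses for about a month, in an order set by the randomization table (Sections 4.8.3 and 4.8.5).

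For the rating scales, Table 4 in Section 11.2 lists one comparative analysis, the effect of lens type, and a menu of tests: "RMANOVA/MANOVA/ Friedman Wilcoxon matched pairs test Tukey HSD post hocs Paired t-test Chi-square test". Period, sequence and lens order are not mentioned.

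For preference: "A Binomial test will be used to analyze the results for the count data of subjective preferences". Answers of no preference "will be evenly distributed to the two options on the basis they would be equally likely to choose either". Preference is asked once, at the visit that ends the second period (Section 4.8.6).

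Three further points bear on how even the two sequences will be:
- Section 4.1.2 states no ratio or blocking in its text and refers to an appendix: "An example of the format generated is given in Appendix 23". That appendix is not available to us.
- Section 4.6.1: "Up to 30 participants will be dispensed / randomized with study products, with a target of 26 completing the study".
- Section 11.1: "The data from the PIANO-2 will be pooled with data from the pilot PIANO study". The pilot's design and its split by lens order are not described.

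**The concern.** In a two-period crossover, any change in ratings between the first and second month (adaptation, season, familiarity with the scale) enters the BT minus UT difference with opposite signs in the two sequences. A lens-only paired analysis leaves it in the error term. If the sequences have unequal numbers of completers, part of it also goes into the lens estimate. The paired t, Wilcoxon and Friedman tests as normally run have no period term, so the choice from the menu matters. Preference has the same exposure, because every participant answers after wearing the second lens. Comfort and dryness ratings and preferences are all primary measures (Section 2), and the plan does not commit to reporting a period estimate from which a reader could judge the matter.

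**Working it through.** **Inputs.** From Section 11.1: two-sided alpha 0.05, power 90%, a difference of 1 comfort unit, total 44 = 18 pilot + 26 PIANO-2. The documents give no SD, no period effect and no sequence split, so these are assumptions. The period effect d (month 2 minus month 1) is run at 0.25, 0.5 and 1.0 unit.

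**Step 1: the plan's own figure.** Without an SD, 44 cannot be reproduced independently. Solving backwards with the noncentral t for a paired test (n = 44, 43 df, difference 1, power 0.90) gives an SD of the paired difference of 2.0. Section 11.1 says only "two-tailed t-test to detect a difference of 1 comfort unit"; read as two-sample with 22 + 22, the per-group SD is 1.0.

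**Step 2: what a period effect does.** Let n1 participants have the sequence in which the period adds d to the BT minus UT difference, and n2 the one in which it subtracts d. Then:
- shift in the unadjusted lens estimate = d × (n1 − n2)/n, zero when n1 = n2;
- the error variance rises by about d² when the sequences are near equal.

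At 26:18, (26 − 18)/44 = 0.182. The shift is 0.09 units for d = 0.5 and 0.18 for d = 1.0, towards or away from BT depending on which sequence is larger.

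**Step 3: unadjusted paired t-test, N = 44, SD 2.0 (simulation).**

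| d | Simple 1:1 randomisation: type I error / power | Fixed 22:22: type I error / power | Fixed 26:18: type I error / power, opposing–favouring |
|---|---|---|---|
| 0.25 | about 5% / 0.90 | 4.9% / 0.897 | 5.1% / 0.868–0.921 |
| 0.5 | about 5% / 0.88 | 4.3% / 0.889 | 5.4% / 0.822–0.936 |
| 1.0 | about 5% / 0.83 | 2.9% / 0.851 | 5.9% / 0.676–0.949 |

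With a period term, power is 0.900 at 22:22 and 0.890 at 26:18 whatever d is. The first column averages over random order, with dropout unrelated to order. The others condition on one split. Under simple randomisation a split of 26:18 or worse has a 29% chance.

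**Step 4: the two-sample reading.** A per-group SD of 1.0 gives a paired-difference SD of √(2(1 − ρ)): 1.4 at ρ = 0 and 1.0 at ρ = 0.5. At 26:18 with the shift opposing the lens effect, unadjusted power is 0.992 / 0.983 / 0.916 against 0.995 adjusted (SD 1.4), and at least 0.99 throughout (SD 1.0). The shift in units is unchanged.

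**Step 5: preference.** Suppose the lenses are equal, there are no ties, and 70% choose the second lens (assumed). With BT first in 26 and second in 18, the expected BT share is (26 × 0.3 + 18 × 0.7)/44 = 20.4/44 = 46.4%; at 60% it is 21.2/44 = 48.2%. Exact binomial type I error for 60% / 70% is 5.1 / 5.6% at 26:18 and 4.4 / 3.1% at 22:22. Averaged over 1:1 random order, each participant's chance of choosing BT is exactly 50%, so the test keeps its size (4.9% at N = 44).

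**Step 6: price of the period term when d = 0 (SD 2.0).** The adjusted standard error is 0.5 × SD × √(1/n1 + 1/n2), with n − 2 df.

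| Split | Unadjusted power | Adjusted power | Loss (points) |
|---|---|---|---|
| 22:22 | 0.900 | 0.8997 | 0.03 |
| 24:20 | 0.900 | 0.897 | 0.3 |
| 26:18 | 0.900 | 0.890 | 1.0 |
| 27:17 | 0.900 | 0.884 | 1.6 |
| 30:14 | 0.900 | 0.855 | 4.5 |
| 13:13 (PIANO-2 alone) | 0.688 | 0.687 | 0.15 |
| 15:11 (PIANO-2 alone) | 0.688 | 0.676 | 1.2 |
| 16:10 (PIANO-2 alone) | 0.688 | 0.663 | 2.5 |

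Under simple randomisation, 30:14 or worse has about a 2% chance at N = 44, and 16:10 or worse a 33% chance at N = 26.

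**The case against.** The strongest reply is that randomisation already does the work. With 1:1 random order and dropout unrelated to it, the order effect is mean-zero noise and both planned tests hold their size; with blocking they become conservative. That stands. A reader might infer from the missing period term that the planned lens comparison is biased or its type I error inflated. The documents do not support this: it needs both a real period effect and a realised imbalance, and they show neither. The schedule format sits in an appendix we cannot see, so absence of blocking cannot be inferred.

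It is also fair that Table 4 lists anticipated procedures, one of which could include period. The defect is that period is not specified, not that it is excluded.

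A material loss of power, about 7 points under simple randomisation, appears only at d = 1.0, a period effect as large as the difference the trial is sized to detect. Participants are adapted wearers (Section 4.6.2) and are trial-fitted with both lenses (Section 4.8.2), which makes that less likely for one-month comfort and dryness. Ratings at insertion, and preference asked after the second lens, are more exposed, but the documents give no figures for them.

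Finally, adjustment is not free: its cost grows with imbalance (Step 6).

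What remains is that the plan leaves open a choice that affects precision and, at an uneven split, the estimate itself.

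**Conclusion.** The point holds as a cheap improvement of low severity. Section 11.2 does not say that period will be modelled for the ratings, and its preference test ignores lens order. On average over a 1:1 random order the planned tests are valid. The expected cost of leaving period out is some power: from 0.900 to about 0.90, 0.88 or 0.83 for period effects of 0.25, 0.5 or 1.0 unit. For the particular split obtained, the lens estimate may also move by d × (n1 − n2)/n in either direction.

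The power figures rest on a back-solved SD of 2.0 and on assumed period effects. If Section 11.1 means a two-sample t-test, the implied SD is smaller and the power loss is small. The preference figures rest on assumed order effects and illustrate direction and scale only.

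**What to change.** **Ratings.** Pre-specify a model with lens and period as fixed effects and participant as a random effect. For complete pairs only, the two-sample t-test on period differences by sequence gives the same lens comparison. The two part company once one-period participants are included, which the missing-data rule in Section 11.2 allows, so the plan should name one as primary. In the pooled analysis, let period differ by study if the pilot's sequence assignments are available; otherwise adjust PIANO-2 and say so. Report the period estimate and the number of completers per sequence.

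**Preference.** Keep the binomial test and add one order-stratified sensitivity analysis, for example Prescott's test, which retains no preference as a category.

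**Cost.** SAP wording and one degree of freedom, or two if period differs by study. PIANO-2 lens order is already in the randomization table; the pooled version also needs the pilot's. The power cost for ratings is in Step 6: at most 1.0 point up to 26:18 at N = 44, more beyond that and for PIANO-2 alone. If a period effect exists and the sequences are balanced, the term gains power instead (0.851 to 0.900 at 22:22 with d = 1.0). The added preference analysis leaves the binomial result unchanged.

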2 OBJECTIVES

The objective of the study is to evaluate the subjective acceptance of Biofinity Toric test lens when worn on a daily wear modality over 1 month.

The primary study measures are:

- Comfort subjective ratings (0-10 scale) and lens preference with respect to comfort (5step Likert)
- Dryness subjective ratings (0-10 scale) and lens preference with respect to dryness (5step Likert)

The secondary study measures are:

Handling subjective ratings (0-10 scale)

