4.8.3 DISPENSING LENS PAIR #1

The participant will be assigned a randomization ID and the first pair (lens pair #1) of contact lenses (either test or control lens) will be selected according to the randomization table.

[figure not shown]
Lens pair #1 will be provided to participants in a manner which does not unmask the participant or investigator, as described in Section 4.7.4.

The lenses will be inserted by the participant.

The contact lenses will be allowed to settle for 10 minutes.

The participant will be asked to give subjective ____ratings (Appendix 9) for:

[figure not shown]
- a) Comfort at insertion (0-10 scale)
- c)
- d) Ease of insertion (0-10 scale)
- a) Lace of incertion (e to ocale)

4.8.4 1-MONTH FOLLOW-UP OF PAIR #1

Participants will be asked to wear lenses for at least 4 hours prior to the visit appointment. Participants who attend without lenses in-situ (wearing lenses) for at least four hours will be rescheduled (unless they report problems when wearing the lenses).

	articipant will be asked to score their subjective responses by reflecting on a typi
day di	uring the previous week of lens wear, includes the following:
0	
0	Overall comfort (0-10 scale)
0	Overall dryness (0-10 scale)
0	Ease of insertion (0-10 scale)
0	Ease of removal (0-10 scale)

The lenses will be removed. Lens disposal procedures are detailed in Section 4.7.6.

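### Four unranked primary measures are each tested at 0.05 with no adjustment and no success rule, so a claim resting on any one of them carries roughly an 8–17% chance of a false difference (4–8% favouring Biofinity Toric) under assumed correlations and tie shares

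*Combined protocol and SAP*

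**What the plan says.** Section 2 (Objectives) lists the primary study measures in two lines, with no order between or within them. The first line is "Comfort subjective ratings (0-10 scale) and lens preference with respect to comfort (5step Likert"). The second repeats the same pair, a rating and a preference, for dryness.

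Section 3 gives the only success wording: the test lens is to have subjective acceptance equal to or better than the control. It names no measure and no any-one or all-of-them rule.

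Section 11.1 bases N on one kind of outcome: "Sample size was calculated using the mean comfort rating data from the previous pilot PIANO study (EX-MKTG-83"). The target is 90% power at two-tailed alpha 0.05 "to detect a difference of 1 comfort unit (scale of 0-10"). It arrives at 44 in total, of whom 18 are pilot completers and 26 are new. It does not say that comfort leads the other measures.

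Section 11.2 says that "Table 4 lists the primary study measures and anticipated statistical procedures", but the table offers a menu of tests by type of variable and sets no hierarchy. Preferences go to a binomial test, and no-preference answers "will be evenly distributed to the two options on the basis they would be equally likely to choose either". The significance level is 0.05 throughout, "with no adjustments for multiple comparisons".

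**The concern.** With four measures of equal standing and no success rule, the choice of headline can be made after the results are seen. A report could present any one significant measure as a primary difference between the lenses, and the chance that at least one of four tests is falsely significant exceeds 5%.

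At the other extreme, if the sponsor means all four to succeed, the error is not inflated, but the chance of success is well below the 90% calculated for the comfort rating. The plan leaves a reader unable to tell which reading applies.

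The point matters more here because 18 of the 44 participants (41%) come from a pilot study whose comfort data were used in planning. A headline measure chosen late would be hard to defend.

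**Working it through.** **1. The plan's own figure.** Inputs from section 11.1: N = 44, power 90%, two-sided alpha 0.05, difference 1 unit. No SD is given, so N cannot be checked independently. For a paired t-test, power = P(T′ > t) with 43 degrees of freedom and noncentrality (1/SD)·√44. Solving for 90% gives SD of the differences = 2.00, a standardised effect of 0.5; noncentrality = 0.5 × 6.633 = 3.32 and power = 90.0%. (A two-sample calculation with 22 per group and SD 1.00 also gives 44.) The split is right: 44 − 18 = 26. These figures concern a comfort rating and nothing else.

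**2. Ceiling.** Four independent tests, each at exactly 5%: 1 − 0.95⁴ = 18.5% for any false difference. In the direction of Biofinity Toric (BT): 1 − 0.975⁴ = 9.6%.

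**3. The planned tests, no lens difference, n = 44.** Simulation of four equally correlated normal within-person differences. Two are analysed by paired t (one of the rating tests in Table 4). Two are turned into preferences and analysed by two-sided exact binomial, with no-preference answers split evenly and an odd one assigned at random. The correlations and no-preference shares are assumptions. Cells show any false difference / one favouring BT.

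| Correlation | No ties | 20% ties | 40% ties | Two ratings alone |
|---|---|---|---|---|
| 0.5 | 16.4 / 8.2% | 13.2 / 6.6% | 10.5 / 5.2% | 9.1–9.4% |
| 0.7 | 14.4 / 7.3% | 11.6 / 5.8% | 9.4 / 4.8% | 8.2–8.5% |
| 0.8 | 13.3 / 6.7% | 10.5 / 5.3% | 8.5 / 4.3% | about 7.8% |
| 0.9 | 11.7 / 5.9% | 8.9 / 4.4% | 7.5 / 3.7% | about 7.0% |

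Simulation error is about ±0.3 point, and the treatment of an odd tie can move a rate by up to about 1 point. Hence roughly 8–17%, and 4–8% favouring BT. Every cell exceeds 5%. On PIANO-2 alone (n = 26), correlations 0.5–0.8 and 0–40% ties give 8.2–13.2% (4.1–6.6% favouring BT).

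**4. Where the excess comes from.** With a share *s* of ties split evenly, the count for one lens has SD √(n(1 − *s*))/2. At n = 44 and *s* = 0.2 this is √35.2/2 = 2.97, but the binomial test assumes √44/2 = 3.32. The preference tests are therefore conservative: actual size about 3% at 20% ties and about 1% at 40%. Example at correlation 0.5: with 20% ties the ratings account for (9.3 − 5)/(13.2 − 5) = 52% of the excess over 5%; with 40% ties, (9.1 − 5)/(10.5 − 5) = 75%. With no ties it is (9.4 − 5)/(16.4 − 5) = 39%. So from about 20% ties upward, the two ratings supply about half or more of it.

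**5. All four required.** Suppose every measure truly shifts by 0.5 SD, with correlations 0.5–0.7 and 20–30% ties. The comfort rating has 90% power, each preference test 70–74%, and all four succeed together in about 51–58% of trials.

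**The case against.** The strongest reply is that the plan promises nothing it fails to deliver. Section 11.2 declines adjustment openly and claims no familywise rate; section 11.1 claims 90% power for a comfort difference only. A reader might infer that whichever success rule is meant, one of the stated figures must be wrong. The documents do not support that: neither figure is contradicted under either reading. What remains is an unstated rule and an uncontrolled any-one claim.

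Second, comfort may be the implied lead because it drives N. That is plausible, but no visible passage says it. If it is the intent, the fix only writes it down.

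Third, section 3 hypothesises equal or better, so a false difference in either direction is not exactly the stated route to success, and half of the two-sided rate favours the control lens. This stands. The 4–8% is the figure that bears on a claim for BT, and the missing definition of equal is a separate matter.

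Fourth, the size depends on two quantities that the documents do not give. This also stands, and is why a range is shown.

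Finally, a reader might count more than four primary tests, since section 4.8.3 also collects "Comfort at insertion (0-10 scale") and Table 3 has columns for 2-week home ratings. The text does not establish this. Section 2 speaks of wear over 1 month, the visible dryness ratings are at the 1-month visits, and the relevant rows and lists are partly blanked out. It does show that the time point of the primary comfort rating needs naming.

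**Conclusion.** The point holds as a gap in error control that should be closed; it is not a contradiction in the plan. Four unranked primary measures, 0.05 for each, no adjustment and no success rule are all plain in the text. If any one may be claimed, the false-difference rate at n = 44 is roughly 8–17%, with 4–8% favouring BT against 2.5% nominal, given correlations of 0.5–0.9, 0–40% no-preference answers, paired t-tests for ratings and the stated binomial test. If all four are required there is no inflation, and joint power of about 51–58% rests on the further assumption of an equal 0.5 SD shift. Confidence in the textual gap is high; confidence in its exact size is moderate.

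**What to change.** Before PIANO-2 data are unmasked:

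1. Name the overall comfort rating (0–10) at the 1-month visit as the single primary measure, at two-sided 0.05. The sponsor should confirm that this is the rating behind N = 44.
2. For the primary measures, replace the no-adjustment sentence with: *If comfort is significant, the 1-month dryness rating and the comfort and dryness preferences are tested with a Holm adjustment at 0.05; otherwise they are reported as supportive, with estimates and 95% confidence intervals.*
3. Show the PIANO-2-only comfort result beside the pooled one, labelled supportive. Naming the primary measure now does not undo knowledge of the 18 pilot completers. This result has about 69% power for 1 unit (n = 26, SD 2.0).

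In simulation with no lens difference, the comfort-first sequence gives 4.9–5.2% for any false claim, treating all 44 as new participants. If comfort truly differs by 0.5 SD and the others do not, false claims on the other three fall from 6.4–14.2% under the plan to 1.0–3.2%.

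**Cost.** Wording and one table. N and the comfort test's 90% power at nominal 0.05 are unchanged. The downside is that dryness and both preferences become descriptive whenever comfort is not significant, which is about 95% of the time if the lenses are truly equal. If the sponsor wants four co-equal primaries, Holm across all four (with the visit named for each) is the alternative; comfort power then falls from 90% to no lower than about 76%, its value at 0.05/4 = 0.0125.
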